7.1. Safety parameters: measuring methods and times

Specific safety parameters for TMS include: past history of epilepsy, pregnancy, other increased neuronal activity in Electroencephalography (EEG), MRI contraindications and substance misuse other than nicotine. Female patients will take a urine pregnancy test before the beginning of the TMS sessions and they will be required to use contraceptive methods during the **study** in order to enroll in the study. In case of a suspicion of a pregnancy during the **study** despite the use of contraceptives a urine test will be taken. These parameters will be observed and are explicit exclusion criteria. EEGs of all patients will be recorded before the beginning of TMS. Patients displaying abnormal EEG findings will be excluded. The rest of above mentioned parameters will be as well observed and are explicit exclusion criteria. After every 5 sessions, assessments of gross motor behaviour (SRRS,

actigraphy) will be repeated. In case of moderate deterioration of motor performance (30% change of initial ratings) patients will be excluded from the **study**.

7.2. Guarantee of follow-up examination of patients in case of adverse reactions.

The study will be carried out according to the protocol. In case of serious adverse events, which may be connected to the TMS **stimulation** or any relevant assessments (Art.42, KlinV), the Ethics Committee will be as soon as possible informed by the sponsor. Serious adverse events may include seizures or exacerbation of psychiatric symptoms. In such cases the TMS sessions will be immediately stopped and the patient will be excluded from the study. A MRI examination will be held and any necessary additional medical consultations will be arranged.

8. Statistics

8.1. Definition of the primary end point and secondary end points

Primary outcome of the study will be clinical response as defined by >30% improvement from the baseline score of the Salpêtrière Retardation Rating Scales (SRRS). Moreover, gross motor behavior (actigraphy), fine motor function (finger tapping test), and hand gesture performance (TULIA) will be assessed at baseline and after the last TMS. Furthermore, we will investigate the efficacy of TMS on disorder specific symptoms; in patients with major depressive disorder, HAMD, MADRS and BDI, in patients with schizophrenia PANSS, SANS, CAINS and the Bush Francis Catatonia Rating Scales will be carried out before and after TMS. Statistical analysis will comprise ANOVAs of motor variables and stimulation mode as between subject variable. Clinical response will be defined as a 30% reduction of the SRRS scores. Frequency of response will be compared between groups using Chi²-Tests.

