Aim The aim of the study is to investigate the effect of TMS at different brain areas on motor functioning in patients with schizophrenia or major depressive disorder (MDD) displaying motor abnormalities. The areas we chose to stimulate, based on an extensive body of research, include Dorsolateral Prefrontal Cortex (DLPFC) and Supplementary Motor Area (SMA)/ Presupplementary Motor Area (pre-) SMA.

Hypothesis We hypothesize that patients with motor abnormalities receiving different configurations of TMS will demonstrate an improvement of motor performance. Across diagnoses, patients with motor retardation will benefit from inhibitory stimulation over SMA/preSMA.

Methods The study design is a single site four arm randomized, sham-controlled trial to unravel the pathophysiology of psychomotor retardation. 80 patients with reduced psychomotor performance will be randomly assigned to four groups (20 patients per group) receiving sessions of TMS of different stimulation parameters. One of the groups will receive sham stimulation. Regardless of the type and the frequency of TMS, the stimulation protocol will consist of 15 daily sessions during a 3 week period.

The four different stimulation conditions include: 1) 15 Hz left dorsolateral prefrontal Cortex (DLPFC) repetitive TMS. 2) 1 Hz SMA/ pre- SMA rTMS. Low frequency TMS has been demonstrated to decrease motor cortex excitability, the motor consequences of which are still to be unraveled. 3) Supplementary Motor Area (SMA)/ Presupplementary Motor Area (pre-)SMA intermittent Thetaburst Stimulation (iTBS). iTBS is a modality of stimulation eliciting an excitatory effect on cortical excitability. 4) Sham stimulation over occipital cortex using a placebo coil, similar to the real one will be used.

Outcome will be evaluated as improvement in gross motor behavior (actigraphy, SRSS), fine motor function (finger tapping test), and hand gesture

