Ghozlan, 1989). The gross motor activity will be furthermore assessed by actigraphs. Actigraphy is a method of quantitative assessment of motor behavior. Patients wear continuously a wrist actigraph, which records the gross motor activity in naturalistic settings. The baseline screening of patients for motor abnormalities will be based on ratings of Bern Psychopathology Scales (BPS), a validated quantitative and qualitative scales for the assessment of system-specific psychotic symptoms of three main domains: motor behavior, language and affectivity.

Fine motor performance The assessment of fine motor performance is based on a finger tapping test, during which, participants are asked to tap their index finger against their thumb as fast as possible in ten seconds. After a short period of practice, three periods will be measured and videotaped. An analysis of the tapping is additionally conducted in slow motion (Barkemeyer et al., 1998).

Gesture Performance The Test of upper limb apraxia (TULIA) (Vanbellingen et al., 2010) is a standardized examination of gesture performance that covers both pantomime and imitation domains and multiple semantic features.

Rationale and aim of the study

Psychomotor retardation is often reported by patients diagnosed with schizophrenia or MDD. Various brain regions may contribute to psychomotor slowing, but the pathophysiology still remains unclear. The effect of TMS of various stimulation parameters at different stimulation sites may lead to improved motor performance. Across diagnoses, patients with motor retardation will benefit from inhibitory stimulation over SMA. Taking into account findings of previous studies, the aims of the study are

- a. To assess the effects of the 3 weeks of daily TMS sessions on motor performance in patients with schizophrenia or MDD (fine motor activity, gross motor activity and gesture performance).
- b. To compare the psychomotor symptoms improvement between different TMS protocols
- c. To assess the effect of daily TMS in different configurations on other non-motor symptoms e.g. depressive symptoms, negative symptoms.

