3.3. Study Hypothesis

Psychomotor symptoms are frequent in schizophrenia and MDD. Various brain regions may contribute to psychomotor slowing, but the precise pathophysiology remains unclear. Patients will be randomly assigned to four groups receiving sessions of TMS in different configurations. After TMS sessions, patients are expected to display an improvement of fine and gross motor activity as well as gesture performance. Across diagnoses, patients with motor retardation will benefit from inhibitory stimulation over SMA. Furthermore, TMS of various stimulation parameters is expected to affect disorder specific symptoms e.g. depressive symptoms and negative symptoms, which will be rated before and after TMS.

4. Study design

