8.2. Planned number of trial subjects with clearly stated justification (power analysis)

When we simulate a distribution of responders, in which two groups get 25% of the responders, the more effective group third group gets 40% and the most ineffective group only 10%, and compare this distribution to an equal distribution of 25% in each group, then the df is 3, noncentrality $\lambda = 14.22$, critical $X = 7.8$ and the effect size $\omega = 0.42$. Thus, we could expect a medium to large effect.

Applying a Chi²-Test with this effect size of $\omega = 0.42$, a significance level of $\alpha = 0.05$, a power of $1-\beta = 0.90$ and a df = 3, then the total required sample size would be 79 subjects. Therefore, each group has to contain at least 20 subjects.

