8.3. Description of the statistical methods foreseen and the planned intermediate assessments

Descriptive data analyses will be performed using Statistical Package for Social Sciences SPSS 17.0® (SPSS Inc., Chicago, IL, USA). In order to compare efficacy of the intervention arms, the primary outcome will be the frequency of patients

achieving response to psychomotor retardation (i.e. >30% improvement from SRRS baseline scores). This group statistic will be calculated using Chi²-Tests.

In order to investigate the effect of rTMS on the psychomotor performance of participants, we will analyze changes in motor variables within and between groups using repeated measures-ANOVAs. This way, we will test for time effects and effects of stimulation protocol. In case of unequal distribution of descriptive parameters between groups, these parameters will be entered as covariates to the repeated measures ANCOVA. Before performing ANOVAs, a normalizing transformation will be carried out if necessary.

The same procedure will be followed in case of the diagnose specific symptoms ratings (BDI, MADRS, Hamilton, PANSS, SANS, CAINS).

To control if a possible improvement of psychomotor performance after rTMS may be attributed to a general clinical response, we will use the analysis of covariance (ANCOVA) with psychomotor performance ratings (before and after TMS) as within subjects factor and changes in ratings of diagnose specific symptoms ratings as covariate.

At three major recruitment steps (25% of total sample, 50% and 75% respectively) we will calculate the primary analysis. If one group proves to have significantly poorer outcome than the others, we will stop this study arm.

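### The four-group chi-square suits the comparison of arms, but a significant result does not by itself support the stated 1 Hz SMA hypothesis, and no contrast, test order or multiplicity rule is given to test it

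*Combined protocol and SAP*

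**What the plan says.** The Hypothesis paragraph of the project summary (section 3) states: "Across diagnoses, patients with motor retardation will benefit from inhibitory stimulation over SMA/preSMA". Sections 3.1 and 3.3 repeat it for SMA, for example "Across diagnoses, patients with motor retardation will benefit from inhibitory stimulation over SMA". Section 2.2 describes low-frequency stimulation as lowering motor cortex excitability and iTBS as excitatory, so the inhibitory arm is 1 Hz. The sentence names no comparator. Section 4.3 labels the sham arm as the control group, and the summary describes the trial thus: "The study design is a single site four arm randomized, sham-controlled trial to unravel the pathophysiology of psychomotor retardation".

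Beside this stand a general expectation that motor performance improves and aim (b) in section 3.1: "To compare the psychomotor symptoms improvement between different TMS protocols".

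On the primary endpoint, response defined as more than 30% SRRS improvement, section 8.1 says "Frequency of response will be compared between groups using Chi²-Tests". Section 8.3 repeats the test for comparing the arms' efficacy. Section 8.2 supplies the degrees of freedom (3) and the assumed pattern, "in which two groups get 25% of the responders, the more effective group third group gets 40% and the most ineffective group only 10" per cent, and concludes "then the total required sample size would be 79 subjects". For the motor variables, section 8.3 says "we will analyze changes in motor variables within and between groups using repeated measures-ANOVAs". Section 8.4 sets p<0.05. None of these sections names a pair of arms, a test order or an adjustment for several tests.

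Section 8.3 also has the primary analysis calculated at 25, 50 and 75% of recruitment, and stops an arm that does significantly worse than the others.

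**The concern.** A four-group chi-square asks whether the response rates differ anywhere among the arms. The hypothesis asks whether one named arm does better, and sham is the natural comparator. The first can be answered yes while the second is false, for instance when DLPFC and iTBS differ and 1 Hz equals sham.

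Alpha is fixed, but the comparison used to judge the 1 Hz hypothesis is not, so it could be chosen after the data are seen. The trial could then report a positive primary result with its only arm-specific hypothesis undecided, or decided by a selected test.

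The interim rule adds to this. It relies on the same label-blind test to find one poorer arm, and it does not exempt sham, the arm the hypothesis would be judged against.

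**Working it through.** **Inputs.** From section 8.2: shares of responders 40/25/25/10%, df 3, alpha 0.05, power 0.90, total 79, 20 per group. The documents give no absolute response rate and do not say which arm holds which share.

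**Assumptions.** Overall response r of 20, 25, 30, 40 or 50%; arm rate = 4 × r × share; 20 per arm; no dropout; Pearson tests; no interim looks unless stated; 400,000 simulated trials per setting.

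**1. The plan's own figure.** w² = [(0.40 − 0.25)² + (0.10 − 0.25)²] / 0.25 = 0.045 / 0.25 = 0.18, so w = 0.424. At 79, noncentrality = 79 × 0.18 = 14.22; the critical value is 7.815 and power 90.1%. Noncentrality of 14.17 is needed for 90%, and 14.17 / 0.18 = 78.7, so 79. The figures reproduce. But w compares how responders are divided among arms with an equal division, so 79 counts responders.

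**2. The same pattern on randomised patients.** For the comparison of response rates in four arms, w² = 0.18 × r / (1 − r). Totals for 90% power are 14.17 / w², about 315, 236, 184, 118 and 79 at r = 20, 25, 30, 40 and 50%. By simulation, 80 patients give the power in the second column below and reach 90% only from r of about 47%.

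**3. Blindness to labels.** The statistic Σ(xᵢ − 20p̄)² / [20p̄(1 − p̄)], with xᵢ the responders in arm i and p̄ the pooled rate, does not change when arms are permuted. At r = 25%, with rates in the order DLPFC, 1 Hz, iTBS, sham, the patterns 0.25/0.40/0.25/0.10 (1 Hz best, sham worst) and 0.40/0.25/0.10/0.25 (1 Hz equal to sham) both give 43% power.

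**4. What a significant four-group test says about 1 Hz versus sham.** The last three columns give the probability that the contrast is significant at 0.05, given a significant four-group test, by the shares held by 1 Hz and sham.

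| r | Four-group power | 40 v 10 | 40 v 25 | 25 v 25 |
|---|---|---|---|---|
| 20% | 0.310 | 0.911 | 0.373 | 0.123 |
| 25% | 0.426 | 0.948 | 0.364 | 0.102 |
| 30% | 0.545 | 0.968 | 0.347 | 0.089 |
| 40% | 0.775 | 0.991 | 0.385 | 0.061 |
| 50% | 0.940 | 0.998 | 0.560 | 0.045 |

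**5. Power of a fixed sequence (four-group test, then contrast).** Multiply the second column by the relevant later column. For 40 v 10: 0.310 × 0.911 = 0.28, then 0.40, 0.53, 0.77 and 0.94. For 40 v 25: from 0.310 × 0.373 = 0.12 to 0.940 × 0.560 = 0.53. The contrast tested alone has power 0.495, 0.623, 0.743, 0.903 and 0.982 (40 v 10), 0.14–0.53 (40 v 25) or 0.19–0.53 (25 v 10).

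**6. Type I error without looks.** Running both tests at 0.05, with either able to claim success, gives 7–8.5% under the complete null. In the sequence, the error for the contrast is about 1.7–1.9% under the complete null and 3.8–4.8% when 1 Hz and sham both hold the 25% share.

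**7. Interim rule (illustration).** The rule needs an assumed reading. Take looks at 5, 10 and 15 per arm, with at most one arm stopped and only a single lowest arm eligible. If it is stopped when the four-group p<0.05, sham at the 10% share is stopped in 16–78% of trials. If it is stopped when that arm differs at 0.05 from the other three pooled, the figure is 25–81%. With such looks, and only patients randomised while both arms were open, the contrast alone at nominal 0.05 has complete-null error of 5.4–7.5% (Pearson) or 2.4–3.3% (Fisher throughout). Using Fisher only after a stop and Pearson otherwise gives 4.5–5.7%.

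**The case against.** The strongest reply is that the primary test does what the plan asks of it. The main objective in section 4.1 is the effect of TMS on psychomotor retardation, none of aims (a) to (c) singles out 1 Hz, and section 8.3 ties the primary outcome to comparing the arms. This stands. A reader might infer that the four-group test is wrong and should give way to 1 Hz versus sham, but the documents do not support that. Replacement would also cost power unless 1 Hz holds the 40% share and sham the 10% share: the primary test would fall from 31–94% to 14–53% at 40 v 25, or to 19–53% at 25 v 10.

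The hypothesis names no comparator, and section 8.3 also mentions changes within groups, so a within-arm reading is open. Sham is therefore an inference, though a natural one, because it is the designated control. The plural in section 8.1 leaves room for pairwise tests, but none is named or ordered.

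A reader might also infer that the significance level is left open. It is not: sections 8.2 and 8.4 fix 0.05. What is missing is the contrast and a rule for several tests.

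Finally, the responder count in 8.2 and the interim rule can be seen as separate matters. They belong here only because they determine what the four-group test can deliver and whether the comparator survives to the end.

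**Conclusion.** The concern holds in this limited form. A significant four-group result does not by itself support the 1 Hz hypothesis, and the plan fixes no comparison that would. The size depends on which arms hold which shares: the contrast agrees with a significant four-group test almost always at 40 v 10, about a third to just over half of the time at 40 v 25, and in 5–12% of trials when 1 Hz and sham are equal. All these figures rest on response rates that the documents do not give.

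The 90% power in 8.2 is right for 79 responders and wrong as a statement about 80 randomised patients unless about 47% or more respond. A reader might infer that 20 per arm is always too few. That does not follow: at 40% overall response the contrast alone has 90% power if the shares are 40 v 10.

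Nor do the documents show that sham will be stopped. The interim percentages come from two assumed readings of a rule that does not say how the poorer arm is found. What is established is that the rule does not exempt sham and that the four-group test cannot identify an arm. This should be fixed; it does not invalidate the comparison of arms.

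**What to change.** 1. **Sections 8.1 and 8.3.** Keep the four-group chi-square as the primary test at 0.05. If it is significant, test 1 Hz SMA/pre-SMA versus sham on more than 30% SRRS response (1 df, two-sided 0.05, once, at the end of the trial). State that the four-group result alone does not support the 1 Hz hypothesis. Label the other pairwise tests and the ANOVAs secondary. Testing the contrast first is an acceptable alternative if fixed in advance.
2. **Section 8.2.** State that 90% applies to 79 responders in a goodness-of-fit test. Give the four-group power for 80 randomised patients (about 31, 43, 55, 78 and 94% at 20, 25, 30, 40 and 50% response). Say which arm is assumed to hold which share, and at what overall response.
3. **Section 8.3, interim rule.** Reconcile it with the sham-controlled design: name the arm-specific comparison that identifies the poorer arm, and say whether the rule covers sham. If an arm of the contrast is stopped, use patients randomised while both arms were open, with one test fixed in advance for all outcomes and shown by simulation to hold 5%. Report the loss of power for all share assignments.

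**Cost.** Wording only, no new data. The price of the sequence is power: both tests are passed in 28, 40, 53, 77 and 94% of trials at 40 v 10, against about 50–98% for the contrast alone, and in 12–53% at 40 v 25. Interim stopping can cost more. At 25 v 10, the contrast alone has 19–53% without looks; with concurrent patients and Fisher's test after a stop, this falls to 15–22% or 10–14% under the two assumed readings. Restating 8.2 means that the sponsor accepts lower power openly or enlarges the arms.

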8.2. Planned number of trial subjects with clearly stated justification (power analysis)

When we simulate a distribution of responders, in which two groups get 25% of the responders, the more effective group third group gets 40% and the most ineffective group only 10%, and compare this distribution to an equal distribution of 25% in each group, then the df is 3, noncentrality $\lambda = 14.22$, critical $X = 7.8$ and the effect size $\omega = 0.42$. Thus, we could expect a medium to large effect.

Applying a Chi²-Test with this effect size of $\omega = 0.42$, a significance level of $\alpha = 0.05$, a power of $1-\beta = 0.90$ and a df = 3, then the total required sample size would be 79 subjects. Therefore, each group has to contain at least 20 subjects.

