3.2. Research Questions, study population

Research Questions

We aim to investigate the effect of TMS in various configurations on psychomotor retardation in patients diagnosed with MDD or schizophrenia. Diagnoses will be given following application of Mini-International Neuropsychiatric Interview (MINI)(Sheehan et al., 1998) and review of the complete cases files. The study consists of a single site four arm randomized, sham-controlled trial. In total, 80 patients will be randomly assigned to four groups (20 patients per group) receiving sessions of TMS of different stimulation parameters. Sham stimulation will be administered in one group. Regardless of the type and the frequency of TMS, the

stimulation protocol will consist of 15 daily sessions during a 3 week period. The four different stimulation conditions have been described above.

Outcome will be evaluated as improvement in gross motor behavior (actigraphy, SRRS), fine motor function (finger tapping test), and hand gesture performance (TULIA). In addition, changes may be demonstrated by the Hamilton Rating Scale for Depression (HAMD) (Hamilton, 1960), Montgomery Åsberg Depression Rating Scale (MADRS) (Montgomery and Asberg, 1979) Beck Depression Inventory (BDI) (Beck et al., 1961), Positive and Negative Syndrome Scales (PANSS) (Kay et al., 1987) and Scales for the Assessment of Negative Symptoms (SANS) (Andreasen, 1983), Clinical Assessment Interview for Negative Symptoms (CAINS) (Kring et al., 2013) and Bush Francis Catatonia Rating Scales (Bush et al., 1996). Clinical ratings will be assessed at baseline and after the last TMS session by a rater blinded to stimulation protocol. Statistical analysis will comprise ANOVAs of motor variables and stimulation mode as between subject variable. Clinical response will be defined as a 30% reduction of the SRRS scores. Frequency of response will be compared between groups using Chi²-Tests.

Study Population

80 in- and outpatients with schizophrenia or major depressive disorder according to DSM-5 displaying reduced levels of motor activity. Diagnoses will be given following application of MINI and review of the complete cases files.

Age: 18-65

Right-handed

Races: all ethnic groups

Gender: male and female. Pregnant patients will be eliminated.

Patients must have normal or corrected-to-normal vision and hearing.

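### Section 8.2 derives N = 79 by counting responders but applies it to patients; for the planned test, under the plan's own responder split, 90% power needs about half of all patients to respond, a rate never stated

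*Combined protocol and SAP*

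**What the plan says.** Section 8.2 describes a scenario "in which two groups get 25% of the responders, the more effective group third group gets 40% and the most ineffective group only 10" per cent, and proposes to "compare this distribution to an equal distribution of 25% in each group". It reports df = 3, noncentrality 14.22, critical value 7.8 and effect size 0.42. With α = 0.05 and power 0.90 it concludes: "then the total required sample size would be 79 subjects". It then sets at least 20 subjects per group. Section 3.2 agrees: "In total, 80 patients will be randomly assigned to four groups (20 patients per group").

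The primary endpoint is binary, an improvement of more than 30% from the baseline SRRS score. Section 8.1 states the analysis: "Frequency of response will be compared between groups using Chi²-Tests". Section 8.3 repeats that "the primary outcome will be the frequency of patients" who respond, compared by chi-square. I found no assumed response rate anywhere in the document, overall or by arm.

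**The concern.** The percentages in Section 8.2 are shares of the responders. They are not response rates within arms. A test of how responders divide over four arms counts responders only; non-responders do not enter it. The sample size from that test is therefore a number of responders, whereas Section 8.2 uses it as a number of patients. The trial will run a different test, a four-arm by response/non-response table on all patients, and its effect size cannot be obtained from responder shares without also knowing how many patients respond.

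This is the only sample-size justification in the plan. If it does not follow, an ethics committee cannot judge whether 80 patients are enough, and a non-significant result could be read as good evidence that the stimulation protocols do not differ when the trial had much less than 90% power to show it.

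**Working it through.** **Inputs.** Responder shares 10/25/25/40% against 25% each, df 3, power 0.90 and α = 0.05 (Section 8.2; α also in 8.4); 20 patients per arm, 80 in total (Section 3.2). The overall response rate p is not in the documents. It is my assumption, varied from 25% to 60%.

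**1. The plan's own figure.** One-sample goodness of fit, four cells:

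- w² = Σ(p₁ − p₀)²/p₀ = (0.15² + 0.15²)/0.25 = 0.18, so w = 0.424
- critical value, chi-square with 3 df at 0.05: 7.815
- noncentrality at N = 79: 79 × 0.18 = 14.22
- power 0.901 at N = 79 and 0.897 at N = 78

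All stated values are reproduced, including the noncentrality to two decimals. In this calculation every counted unit is a responder.

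**2. Can 79 responders occur?** 40% of 79 is 31.6 responders in an arm of 20 patients. With this split, the most the trial can produce is 20/0.40 = 50 responders, an overall rate of 50/80 = 62.5%.

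**3. The test that is planned.** With equal arms and overall response rate p, an arm holding share s of the responders has response rate 4sp. The arm rates are 0.4p, p, p and 1.6p. For the 4×2 table:

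- w² = ¼ × [(0.6p)² + 0 + 0 + (0.6p)²] / [p(1 − p)] = 0.18 × p/(1 − p)

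This equals 0.18 only when p = 50%. It is smaller below 50% and larger above.

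**4. Power with 80 patients.** The asymptotic figures use the noncentral chi-square with 3 df and noncentrality 80w². The exact figures come from enumerating all 21⁴ = 194,481 possible outcomes of the Pearson test with 20 per arm. The last column is the asymptotic N for 90% power, before rounding up to equal arms.

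| Overall p | Arm rates (%) | 80w² | Power, asymptotic | Power, exact | N for 90% |
|---|---|---|---|---|---|
| 25% | 10/25/25/40 | 4.80 | 42% | 43% | 237 |
| 30% | 12/30/30/48 | 6.17 | 53% | 55% | 184 |
| 35% | 14/35/35/56 | 7.75 | 64% | 66% | 147 |
| 40% | 16/40/40/64 | 9.60 | 74% | 78% | 119 |
| 45% | 18/45/45/72 | 11.78 | 83% | 87% | 97 |
| 50% | 20/50/50/80 | 14.40 | 90.5% | 94% | 79 |
| 55% | 22/55/55/88 | 17.60 | 95.5% | 98% | 65 |
| 60% | 24/60/60/96 | 21.60 | 98% | >99% | 53 |

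Power reaches 90% at p = 49.6% (asymptotic) or 46.8% (exact).

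**5. Other readings.**

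- If the final test were the one modelled in Section 8.2, on responders only, p = 50% gives 40 responders, noncentrality 40 × 0.18 = 7.2 and power 60%. The maximum of 50 responders gives 50 × 0.18 = 9.0 and power 71%. It never reaches 90%.
- If 10/25/25/40% were meant as response rates within arms, that is the p = 25% row: power 42–43%.

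**The case against.** The arithmetic in Section 8.2 is correct. Its last step, a chi-square test with w = 0.42 and df 3 needing 79 subjects, is also valid for a 4×2 table that really has that w; in such a table N does count all patients. That stands. The fault lies in where w came from: a different table, and carrying it over requires p = 50%.

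No loss of power is shown, because nothing in the documents puts the response rate below half. That also stands. At about half or more, the claim holds or is conservative. What is shown is that the claim depends on a specific assumption, with one arm at 20% and another at 80%, that is nowhere declared.

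The threshold of about half holds only for the responder split in Section 8.2. Arm rates of 10/25/25/65%, for instance, average 31% and give 93% power (94% exact). This is a fair limit on the claim, but the split held fixed here is the plan's own.

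The plan names chi-square tests without spelling out a 4×2 table. Comparing response frequency between groups is most naturally that table, and the responder-only alternative gives the plan less power.

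Finally, the power figures assume a single analysis with four full arms of evaluable patients. Section 8.3 plans looks at 25%, 50% and 75% of recruitment with possible stopping of an arm, and Section 8.5 calls for complete records only but also for ITT with LOCF. The table does not cover these features. Section 8.2 does not either, so the comparison with its 90% is on the same basis.

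**Conclusion.** The concern holds. The figure of 79 counts responders, is applied to patients, and does not establish 90% power for the planned primary test. Under the plan's own responder split and a single analysis of 80 evaluable patients, 90% power requires an overall response of about 47–50% or more. At 45% the exact shortfall is about 3 percentage points (87% against 90%). At 40% or below, power is under 80%, and at 25% it is less than half the stated figure. The response rates in this range are assumptions, since the documents supply none; whether the trial is in fact underpowered cannot be settled from them. The statement should be corrected because the plan's only power claim cannot be verified as written.

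**What to change.** Rewrite Section 8.2 for the test that will be run: four arms by response/non-response among all patients, chi-square with df 3, α = 0.05, 20 per arm. State the assumed response rate in each arm, with its basis, and the power that 80 patients give under it. Add a short table of power over overall response rates of 25% to 60%, such as the one above, and say that it assumes one analysis, four complete arms and 80 evaluable patients. Remove the unconditional statement that 79 subjects give 90% power, unless arm rates of about 20/50/50/80% are explicitly assumed.

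The cost is rewording one section; the planned test and the sample size can stay as they are. The stated power may become less favourable. If the sponsor's credible response rate is clearly below half, the sponsor will have to choose between declaring lower power and enrolling more patients (119 at 40%, 184 at 30%). The rewrite makes that choice visible without dictating it.
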